5.8.5.3. Medications Not Permitted for Doses Above 300 mg BID

As described in [Section 1.2.2](#), PF-06882961 is a reversible inhibitor of CYP2C8 and UGT1A1 and is a weak time- and NADPH-dependent inhibitor of CYP3A4/5. As such, PF-06882961 at doses where projected AUC₂₄ exposure is expected to exceed approximately 7392 ng.h/mL should not be administered with drugs that are primarily metabolized by these enzymes.

Based on preliminary modeling of PK data emerging from the ongoing FIH study, this AUC₂₄ is currently predicted to be achieved at PF-06882961 doses exceeding 300 mg BID ([Table 4](#)). Therefore, for cohorts administered doses of PF-06882961 above 300 mg BID only (this dose level may be refined based on emerging data from this study), subjects on a background therapy (for example, for treatment of hypertension or dyslipidemia) which is known to have a high risk of DDI through CYP3A, CYP2C8 or

UGT1A1, must switch to another acceptable treatment, as determined by the subject's physician or the PI, ***at least 4 weeks prior to Day 1*** (a non-exhaustive list of such medications is provided in [Appendix 2](#)). In addition, subjects must be in a stable condition, conforming to all Inclusion/Exclusion criteria (see [Section 4.1](#) and [Section 4.2](#)).

5.9. Rescue Medication

There is no rescue therapy to reverse any AEs observed with administration of IP; standard medical supportive care must be provided to manage the AEs (see [Section 5.8.4](#) for management of nausea and vomiting).

For medical management of hypoglycemia, the investigator may administer oral carbohydrate, glucagon, or IV glucose according to his or her medical judgment. At a minimum however, treatment or administration of a scheduled meal should be given if glucose falls <60 mg/dL for at least 15 minutes, irrespective of whether the subject exhibits symptoms. Investigators may choose to administer treatment sooner if subjects have bothersome symptoms of hypoglycemia along with glucose values of ≤ 70 mg/dL.

No rescue therapy will be provided for hyperglycemia. If a subject has sustained elevated fasting plasma glucose concentrations that are >270 mg/dL on 3 consecutive measurements over 3 days, that subject will be discontinued, and the investigator will recommend further appropriate glycemic treatment according to the local healthcare standards and national guidelines.

6. STUDY PROCEDURES

6.1. Proposed Chronology of Procedures

For the study period described below, when multiple procedures are scheduled at the same time point(s) relative to dosing, the following chronology of events should be adhered to, ***where possible***.

- *ECGs*: obtain prior to vital sign measurements and as close as possible to the scheduled time, but prior to blood specimen collection (refer to [Section 7.1.5](#));
- *Vital Signs (BP and pulse rate)*: obtain as close as possible to the scheduled time, but prior to blood specimen collection (refer to [Section 7.1.4](#));
- *Fasting blood samples*: after assessment of 12-lead ECG and vital signs but prior to dosing;
- *PK blood specimens*: obtain at the scheduled time (refer to [Section 7.2.1](#));
- *Other pre-dose procedures*: obtain all other procedures as close as possible to the scheduled time, but may be obtained before or after blood specimen collection;
- *Dosing*: must occur at the scheduled nominal time (refer to [Section 5.5](#)) and following predose blood sample collection.

- ***If*** an IV catheter is placed for serial blood sample collections, ECGs and vital signs (pulse rate, BP) assessments should be either collected prior to the insertion of the catheter or sufficient rest period after catheter insertion introduced to minimize impact of catheter placement on these assessments.

6.2. Screening

Refer to the [Schedule of Activities](#) for the study procedures to be completed at the screening visit. A signed and dated ICD will be obtained from each subject at the screening visit before performing any protocol-specific procedures.

Subjects will be screened within 28 days prior to administration of the blinded IP to confirm that they meet the subject selection criteria for the study. The investigator (or an appropriate delegate at the investigator site) will obtain informed consent from each subject in accordance with the procedures described in [Section 1.2.3](#).

A subject who qualified for this protocol but did not enroll from an earlier cohort/group may be used in a subsequent cohort/group for this study. Subjects may be re-screened and all screening procedures must be repeated and the subject assigned a new 8-digit study-specific subject identification number (SSID) number. This criterion would also apply to subjects who screened for this study more than 28 days prior to dosing.

To prepare for study participation, subjects will be instructed on the information in [Section 4.4](#) and [Section 5.8](#) of the protocol.

6.3. Study Period

Refer to the [Schedule of Activities](#) for the study procedures to be completed during the Study Period.

CCI

If a subject has any clinically significant, study-related abnormalities at the conclusion of a scheduled inpatient portion of the study, the Pfizer medical monitor (or designated representative) should be notified and the subject may be asked to remain in the CRU until such abnormalities are deemed not clinically significant, or it is safe for outpatient follow-up. If the subject is unable or unwilling to remain in the CRU and/or when outpatient follow-up is deemed appropriate, the Pfizer medical monitor (or designated representative) should be so notified, and the investigator should make every effort to arrange follow-up evaluations at appropriate intervals to document the course of the abnormalities.

6.4. Follow-up

6.4.1. Follow-up Visit

Subjects will return to the CRU 7 to 14 days following the last dose of IP for a Follow-up visit. Refer to the [Schedule of Activities Table 1](#) and [Table 2](#) for the study procedures to be completed at this visit.

6.4.2. Follow-up Contact

Follow-up contact will be completed at least 28 calendar days and up to 35 calendar days after the last administration of the investigational product to capture any potential AEs (see [Section 8.1.4](#)) and to confirm appropriate contraception usage (see [Section 4.4.4](#)). Contact with the subject may be done via a phone call.

6.5. Subject Withdrawal/Early Termination

Withdrawal of consent:

Subjects who request to discontinue receipt of study treatment will remain in the study and must continue to be followed for protocol-specified follow-up procedures. The only exception to this is when a subject specifically withdraws consent for any further contact with him or her or persons previously authorized by the subject to provide this information. Subjects should notify the investigator in writing of the decision to withdraw consent from future follow-up, whenever possible. The withdrawal of consent should be explained in detail in the medical records by the investigator, as to whether the withdrawal is only from further receipt of investigational product or also from study procedures and/or post-treatment study follow-up, and entered on the appropriate CRF page. In the event that vital status (whether the subject is alive or dead) is being measured, publicly available information should be used to determine vital status only as appropriately directed in accordance with local law.

Lost to follow-up:

All reasonable efforts must be made to locate subjects to determine and report their ongoing status. This includes follow-up with persons authorized by the subject as noted above. All attempts should be documented in the subject's medical records. If it is determined that the subject has died, the site will use locally permissible methods to obtain the date and cause of death. If the investigator's use of a third-party representative to assist in the follow-up portion of the study has been included in the subject's informed consent, then the investigator may use a sponsor-retained third-party representative to assist site staff with obtaining the subject's contact information or other public vital status data necessary to complete the follow-up portion of the study. The site staff and representative will consult publicly available sources, such as public health registries and databases, in order to obtain updated contact information. If, after all attempts, the subject remains lost to follow-up, then the last-known-alive date as determined by the investigator should be reported and documented in the subject's medical records.

Subjects may withdraw from the study at any time at their own request, or they may be withdrawn at any time at the discretion of the investigator or sponsor for safety (see also [Section 8.1.3](#)) or behavioral reasons, or the inability of the subject to comply with the protocol-required schedule of study visits or procedures at a given investigator site. The early termination visit applies only to subjects who are randomized and then are prematurely withdrawn from the study.

If a subject does not return for a scheduled visit, every effort should be made to contact the subject. The investigator or site staff should attempt to contact the subject twice. After 2 attempts, CRU staff may send a registered letter. If no response is received from the subject, the subject will be considered lost to follow-up. All attempts to contact the subject and information received during contact attempts must be documented in the subject's medical record. In any circumstance, every effort should be made to document subject outcome, if possible. The investigator should inquire about the reason for withdrawal, request that the subject return for a final visit, if applicable, and follow up with the subject regarding any unresolved AEs.

It may be appropriate for the subject to return to the clinic for final safety assessments to be scheduled as early as practically feasible following the decision to withdraw from the study. Subjects should be questioned regarding their reason for withdrawal. At the early-withdrawal visit, every effort must be made to complete the following assessments:

- Full physical examination, if there is a new or open AE or clinically significant abnormal physical finding from the last visit;
- Supine BP and pulse rate measurements;
- 12-Lead ECG measurement;
- Blood and urine specimens for safety laboratory tests;
- Blood sample for PK analysis.

Lack of completion of all or any of the withdrawal/early termination procedures will not be viewed as protocol deviations so long as the subject's safety was preserved.

If the subject withdraws from the study and also withdraws consent for disclosure of future information, no further evaluations should be performed and no additional data should be collected. The sponsor may retain and continue to use any data collected before such withdrawal of consent.

Subjects who withdraw from the study may be replaced at the discretion of the investigator upon consultation with the sponsor provided that the nature of the safety event does not preclude dose escalation and that exposure stopping limits are observed.

7. ASSESSMENTS

Every effort should be made to ensure that protocol-required tests and procedures are completed as described. However, it is anticipated that from time to time there may be circumstances outside the control of the investigator that may make it unfeasible to perform the test. In these cases, the investigator must take all steps necessary to ensure the safety and well-being of the subject. When a protocol-required test cannot be performed, the investigator will document the reason for the missed test and any corrective and preventive actions that he or she has taken to ensure that required processes are adhered to as soon as possible. The study team must be informed of these incidents in a timely manner.

For samples being collected and shipped, detailed collection, processing, storage, and shipment instructions and contact information will be provided to the investigator site prior to initiation of the study.

7.1. Safety

7.1.1. Laboratory Tests

The following clinical laboratory tests will be performed at times defined in the [Schedule of Activities](#) section of this protocol. Additional laboratory results may be reported on these samples as a result of the method of analysis or the type of analyzer used by the clinical laboratory; or as derived from calculated values. These additional tests would not require additional collection of blood. Unscheduled clinical laboratory measurements may be obtained at any time during the study to assess any perceived safety concerns.

Table 7. Safety Laboratory Tests

Hematology	Chemistry	Urinalysis	Other
Hemoglobin	BUN/urea	pH	FSH ^b
Hematocrit	Creatinine	Glucose (qual)	Urine drug screening
RBC count	Plasma glucose (fasting)	Protein (qual)	HIV ^c
MCV	Calcium	Blood (qual)	HepBsAg ^c
MCH	Sodium	Ketones	HepBcAb ^c
MCHC	Potassium	Nitrites	HCVAb ^c
Platelet count	Chloride	Leukocyte esterase	HbA1c
WBC count	Total CO ₂ (bicarbonate)	Urobilinogen	C-peptide ^d
Total neutrophils (Abs)	AST	Urine bilirubin	
Eosinophils (Abs)	ALT	Microscopy ^a	
Monocytes (Abs)	Total bilirubin		
Basophils (Abs)	Alkaline phosphatase		
Lymphocytes (Abs)	Uric acid		
PT/INR/aPTT	Albumin		
	Total protein		
	Serum total bile acids ^d		
	Additional Tests (Needed for Hy's Law)		
	AST, ALT (repeat)		
	Total bilirubin (repeat)		
	Albumin (repeat)		
	Alkaline phosphatase (repeat)		
	Direct bilirubin		
	Indirect bilirubin		
	Creatine kinase		
	GGT		
	PT/INR		
	Total bile acids		
	Acetaminophen drug and/or protein adduct levels		

- a. Only if urine dipstick is positive for blood, protein, nitrites or leukocyte esterase.
- b. For female subjects to confirm post-menopausal status only; at screening.
- c. At Screening only.
- d. Assessed at Screening for exclusion, but also as part of MMTT.

- The minimum requirement for drug screening includes cocaine, tetrahydrocannabinol (THC), opiates/opioids, benzodiazepines, and amphetamines.
- In addition to the clinical laboratory tests listed in Table 7, blood samples will be drawn and analyzed for calcitonin, amylase, lipase, lipid panel, TSH and FT4 at the time points listed in Table 1 and Table 2 in the Schedule of Activities. Review of these data is not required prior to dose escalation in each cohort, cumulative results will be reviewed as they become available.

Any remaining serum/plasma from samples collected for clinical safety laboratory measurements at baseline and at all times after dose administration may be retained and stored for the duration of the study. Upon completion of the study, these retained safety samples may be used for the assessment of exploratory safety biomarkers or unexpected safety findings. These data will not be included in the clinical study report (CSR). Samples to be used for this purpose will be shipped to either a Pfizer-approved BBS facility or other designated laboratory and retained for up to 1 year following the completion of the study.

7.1.2. Physical Examinations

Physical examinations should be performed at nominal time points specified in the [Schedule of Activities](#) of this protocol.

Physical examinations may be conducted by a physician, trained physician's assistant, or nurse practitioner as acceptable according to local regulation. A full physical examination will include head, ears, eyes, nose, mouth, skin, heart and lung examinations, lymph nodes, and gastrointestinal, musculoskeletal, and neurological systems. The limited or abbreviated physical examination will be focused on general appearance, the respiratory and cardiovascular systems, and subject-reported symptoms.

7.1.3. Body Weight

Body weight measurements will be obtained at the time points outlined in the [Schedule of Activities](#). If possible, the same scale should be used for a particular subject for all body weight measurements obtained at the CRU. For measuring weight, a scale with appropriate range and resolution is used and must be placed on a stable, flat surface.

Body weight will be measured at outpatient visits to the study site as listed in [Table 1](#) of the [Schedule of Activities](#) under the following conditions:

- After void of urine;
- After removal of shoes, bulky layers of clothing, and jackets so that only light clothing remains;
- While remaining still during measurement.

During admission to the CRU, body weight will be measured at the time points listed in [Table 2](#) of the [Schedule of Activities](#). Measurement will be taken under the following conditions:

- In the morning, prior to eating and drinking;
- After the subject has been asked to void;
- While wearing only a hospital gown and no shoes;
- While remaining still during measurement.

7.1.4. Blood Pressure and Pulse Rate

BP and pulse rate will be measured at times specified in the [Schedule of Activities](#) section of this protocol. Additional collection times, or changes to collection times, of BP and pulse rate will be permitted, as necessary, to ensure appropriate collection of safety data.

Supine BP will be measured with the subject's arm supported at the level of the heart, and recorded to the nearest mmHg after approximately 5 minutes of rest. The same arm (preferably the dominant arm) will be used throughout the study. Subjects should be instructed not to speak during measurements. When triplicate BP and pulse rate are required, they will be obtained approximately 2 to 4 minutes apart; the average of the triplicate BP and pulse rate measurements collected at each nominal time point on Day -1 will serve as each subject's time-controlled baseline values.

The same properly sized and calibrated BP cuff will be used to measure BP each time. The use of an automated device for measuring BP and pulse rate is acceptable; however, when done manually, pulse rate will be measured in the brachial/radial artery for at least 30 seconds. When the timing of these measurements coincides with a blood collection, BP and pulse rate should be obtained prior to the nominal time of the blood collection (refer to [Section 6.1](#)).

7.1.5. Electrocardiogram

12-Lead ECGs should be collected at times specified in the [Schedule of Activities](#) section of this protocol.

All scheduled ECGs should be performed after the subject has rested quietly for at least 10 minutes in a supine position. When a meal or snack is scheduled at the same time as an ECG, the ECG must be performed prior to the meal/snack.

Triplicate 12-lead ECGs will be obtained approximately 2 to 4 minutes apart; the average of the triplicate ECG measurements collected at each nominal time point on Day -1 will serve as each subject's time-controlled baseline QTcF value.

To ensure safety of the subjects, a qualified individual at the investigator site will make comparisons to baseline measurements.

If the QTcF interval is increased by ≥ 45 msec from the baseline, or an absolute QTcF value is ≥ 500 msec for any scheduled ECG, then 2 additional ECGs will be collected, approximately 2 to 4 minutes apart, to confirm the original measurement. If either of the QTcF values from these repeated ECGs remains above the threshold value (ie, is ≥ 45 msec from the baseline, or is ≥ 500 msec), then a single ECG must be repeated at least hourly until QTcF values from 2 successive ECGs fall below the threshold value that triggered the repeat measurement.

Further ECG monitoring will occur if a) the mean value from the triplicate measurements for any post-dose QTcF interval is increased by ≥ 30 msec from the baseline **and** is >450 msec; or b) an absolute QTcF value is ≥ 500 msec for any scheduled ECG. If either of these conditions occurs, then single ECG measurements must be repeated at least hourly until QTcF values from 2 successive ECGs fall below the threshold value that triggered the repeat measurement.

If QTcF values remain ≥ 500 msec (or ≥ 30 msec from the baseline **and** >450 msec) for greater than 4 hours (or sooner, at the discretion of the investigator), or QTcF intervals get progressively longer, the subject should undergo continuous ECG monitoring. A cardiologist should be consulted if QTcF intervals do not return to less than 500 msec (or to <45 msec above the baseline) after 8 hours of monitoring (or sooner, at the discretion of the investigator).

ECG data will be submitted to a central laboratory for overread measurement of ECG intervals and overall interpretation. The central ECG laboratory will be blinded to treatment allocation. The final ECG report from the central laboratory should be maintained in the subject's source documentation and be the final interpretation of the ECG recording.

In some cases, it may be appropriate to repeat abnormal ECGs to rule out improper lead placement or technical aberration as contributing to the ECG abnormality. It is important that leads are placed in the same positions each time in order to achieve precise ECG recordings. If a machine-read QTcF value is prolonged, as defined above, repeat measurements may not be necessary if a qualified medical provider's interpretation determines that the QTcF values are in the acceptable range.

7.1.6. Glucometer Monitoring of Glucose

Investigators will monitor FSBG using glucometer measurements at the times specified in the [Schedule of Activities](#). FSBG measurements should be taken before breakfast while the subject is confined to the CRU.

FSBG readings will be maintained at the sites in source documents, and only the glucose results from the laboratory will be reported in the study database. The sites may share the FSBG readings with the Sponsor for the purpose of dose-escalation decisions, but these data will be stored in the sites' source documents unless related to an AE as described below.

Specifically, if an FSBG result is ≤ 70 mg/dL, a second FSBG should be obtained to confirm the glucose value, in addition to a venous sample that will be sent to the clinical laboratory for confirmation. If the value from this second FSBG is also ≤ 70 mg/dL, the second value will be recorded as a hypoglycemic AE. FSBG will continue to be monitored until the glucose value returns to >70 mg/dL. Samples may be taken more frequently if deemed necessary by the investigator. FSBG readings from a glucometer are permitted at any time if the investigator or subject notes symptoms of hypoglycemia.

7.1.7. Hypoglycemia Reporting

Hypoglycemia will be assessed and reported in several categories: severe hypoglycemia, documented symptomatic hypoglycemia, asymptomatic hypoglycemia, and probable hypoglycemia.

Severe hypoglycemia: In order to be considered severe hypoglycemia all of the following criteria must be met:

- The subject required the assistance of another person to actively administer carbohydrate, glucagon, or other resuscitative actions.
- The subject exhibited at least one of the following neurological symptoms:
 - Memory loss;
 - Uncontrollable behavior;
 - Irrational behavior;
 - Unusual difficulty in awakening;
 - Suspected seizure;
 - Seizure;
 - Loss of consciousness.
- The subject had one of the following:
 - Blood glucose <50 mg/dL, or
 - If blood glucose was not measured, the clinical manifestations were reversed by carbohydrate administration.

Documented symptomatic hypoglycemia: An event during which typical symptoms of hypoglycemia are accompanied by a measured glucose concentration ≤ 70 mg/dL.

Asymptomatic hypoglycemia: An event not accompanied by typical symptoms of hypoglycemia but with a measured glucose concentration ≤ 70 mg/dL.

Probable symptomatic hypoglycemia: An event, during which typical symptoms of hypoglycemia are not accompanied by a “real time” glucose determination, but were presumably caused by a plasma glucose concentration ≤ 70 mg/dL. The clinical picture must include prompt resolution with oral carbohydrates, subcutaneous glucagon, or intravenous glucose.

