6.2.1.1. Hypoglycemia Monitoring

Hypoglycemia AEs will be recorded in the Case Report Form (CRF) as a separate page. Details of when these will be recorded are given in the protocol Section 7.1.7.

For programming purposes, the hypoglycemic AE categories are based on the following:

- Severe Hypoglycemia: Severe is checked in the severity criteria of the CRF. This assessment will be made by the PI based on the protocol definition.
- Documented Symptomatic Hypoglycemia: If (1 – Did the subject have symptoms of hypoglycemia?) Yes and (2 – Was the blood glucose measured?) Yes and result \leq 70 mg/dL on the CRF, but hypoglycemia is not classified as severe.
- Asymptomatic Hypoglycemia: If (1) No and (2) Yes and result \leq 70 mg/dL on the CRF, but hypoglycemia is not classified as severe.

- Probable Symptomatic Hypoglycemia: If (1) Yes and (2) No and (2b – If blood glucose was not measured, did symptoms resolve when treated with carbohydrate or glucagon?) Yes on the CRF, but hypoglycemia is not classified as severe.

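### Severe hypoglycemia: when glucose was not measured, only reversal by carbohydrate counts, although glucagon is accepted everywhere else in the classification

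*Protocol*

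**What the plan says.** Protocol 7.1.7 sets up four hypoglycemia classes. For the severe class the rule is conjunctive: "In order to be considered severe hypoglycemia all of the following criteria must be met".

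- **Criterion 1, assistance:** "The subject required the assistance of another person to actively administer carbohydrate, glucagon, or other resuscitative actions".
- **Criterion 2:** at least one neurological symptom from a list that includes seizure and loss of consciousness.
- **Criterion 3, evidence that glucose was low:** either a measured value below 50 mg/dL or, in the second branch, "If blood glucose was not measured, the clinical manifestations were reversed by carbohydrate administration".

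For probable symptomatic hypoglycemia, the class for symptomatic events without a contemporaneous glucose value, the same section says: "The clinical picture must include prompt resolution with oral carbohydrates, subcutaneous glucagon, or intravenous glucose".

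SAP 6.2.1.1 turns this into programming rules. An event is severe if severe is checked on the CRF, and on that check it says: "This assessment will be made by the PI based on the protocol definition". An event is probable symptomatic if there were symptoms, glucose was not measured, CRF item 2b is answered yes, and the event was not classified as severe. Item 2b asks: "did symptoms resolve when treated with carbohydrate or glucagon".

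Protocol 5.9 foresees glucagon as a possible treatment: "the investigator may administer oral carbohydrate, glucagon, or IV glucose according to his or her medical judgment".

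**The concern.** Criteria 1 and 3 of the severe definition do not name the same agents. Glucagon proves that assistance was needed, but recovery after glucagon does not count as evidence that the episode was hypoglycemia. The probable symptomatic class, which is the milder one, accepts exactly that evidence. The documents give no reason for the difference.

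Two things are at stake. First, an assisted neurological event can be labelled one class too low. Compared with a third criterion that names glucagon, the present wording can only take events out of the severe class, never add any. Second, classification may vary between sites. The study uses roughly 2 to 5 sites (Protocol 3.1). One investigator may apply the wording literally, and another may tick severe because the event plainly was. Adverse events are a primary endpoint, and hypoglycemic events are tabulated by class (Protocol 9.7.3, SAP 8.4.5), so the definition should give one answer for one event.

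**Working it through.** The plan states no figure on this point, so there is none to reproduce. The check sets the rules side by side and runs test cases through them.

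**Step 1. Agents each rule accepts**

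| Rule | Carbohydrate | Glucagon | Other resuscitative action |
|---|---|---|---|
| Severe, criterion 1 (Protocol 7.1.7) | yes | yes | yes |
| Severe, criterion 3, glucose not measured (Protocol 7.1.7) | yes | **no** | no |
| Probable symptomatic (Protocol 7.1.7) | yes (oral, or intravenous glucose) | yes | no |
| CRF item 2b (SAP 6.2.1.1) | yes | yes | no |

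Glucagon is accepted in three of the four rows.

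**Step 2. Test cases.** Every case has third-party assistance (criterion 1 met), a listed neurological symptom (criterion 2 met) and typical symptoms. Only the glucose status and the reversing agent vary.

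| Case | Glucose | Reversed by | Criterion 3 | Class on the literal text |
|---|---|---|---|---|
| 1 | measured, <50 mg/dL | any agent | met | severe |
| 2 | not measured | carbohydrate, including IV glucose | met | severe |
| 3 | not measured | glucagon alone | **not met** | **probable symptomatic** |
| 4 | not measured | glucagon and carbohydrate | met if reversal is credited to the carbohydrate | severe or probable symptomatic |
| 5 | not measured | other resuscitative action only | not met | neither severe nor probable symptomatic |

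Cases 2 and 3 differ only in the agent, yet they fall in different classes. Case 4 depends on which agent is given the credit.

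**Step 3. Does the SAP repair case 3?** No. If the investigator follows the protocol definition, severe is not ticked. Item 2b is answered yes, and the SAP rule then yields probable symptomatic. Item 2b combines both agents in one question, so that item alone cannot identify the affected events afterwards.

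**Step 4. Size if one such event occurred.** Each cohort has 9 active subjects (Protocol 9.1). One event of the case 3 type changes the severe count at that dose from 1/9 = 11.1% to 0/9 = 0%, and the probable symptomatic count from 0/9 to 1/9. Total hypoglycemia incidence stays at 1/9. These figures are conditional on one assumed event, and the documents give no expected rate from which to derive a probability.

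**The case against.** The strongest objection is that the case hardly arises here. Subjects stay in the unit from Day -2 to Day 30. The last blood sample is 48 hours after the Day 28 morning dose. Under BID dosing that is 48 − 10 = 38 hours after the final evening dose. The longest mean half-life in Protocol Tables 3 and 4 is 5.78 h, and 38/5.78 = 6.6, so more than six half-lives pass under observation (taking preliminary data from healthy subjects as a guide). The minimum treatment rule and the earlier-treatment option for hypoglycemia in Protocol 5.9 both presuppose a glucose value. Insulin and sulfonylureas are prohibited (5.8.5.1, 5.8.5.2), and Protocol 1.3.1 says the drug class does not typically cause hypoglycemia without such agents. This stands and sets the priority. It does not remove the inconsistency: Protocol 7.1.6 permits a glucometer reading when symptoms are noted but does not require one, and 7.1.7 itself provides for unmeasured events.

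Several stronger readings are tempting, and the documents do not support them.

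- **A reader might infer that the SAP downgrades these events by program.** It does not. Severe comes from the investigator's tick, nothing re-tests the three criteria, and a severe tick takes precedence. The outcome depends on how literally the investigator reads the definition.
- **A reader might infer that any subject unable to swallow is excluded from the severe class.** Criterion 3 does not limit carbohydrate to the oral route, and the same section specifies oral where it means oral. Recovery after IV glucose therefore qualifies. The gap is reversal by glucagon alone with no glucose reading.
- **A reader might infer that the event disappears from the safety assessment or weakens escalation.** It is still an AE with intensity graded under Protocol 8.3. Protocol 8.2.3 names convulsions without hospitalization among its examples of important medical events. The halting rules in 3.2 do not refer to the 7.1.7 classes; they use severe AEs, SAEs, clinically significant abnormalities and exposure limits.

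**Conclusion.** The inconsistency is real but minor. On the literal text, an assisted event with a listed neurological sign, no glucose measurement and reversal by glucagon alone cannot be severe and becomes probable symptomatic. Because the class rests on the investigator's reading of that text, identical events may also be classified differently across sites.

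The effect is one label in a descriptive hypoglycemia table. It is expected to be very rare, and its frequency cannot be estimated from the documents. The 11.1% to 0% shift is an illustration for one assumed event, not evidence of a bias in the trial's results.

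The conclusion assumes that investigators apply 7.1.7 as written and that the CRF severity section, which is not among the documents, follows the protocol wording. If the form already names glucagon there, only the protocol text is out of step.

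**What to change.** Reconcile Protocol 7.1.7 with itself and with SAP 6.2.1.1, so that the unmeasured-glucose branch of the third severe criterion names glucagon beside carbohydrate. It would then agree with criterion 1, the probable symptomatic definition and CRF item 2b. No route needs to be added for carbohydrate. While doing so, the sponsor should state how an unmeasured event reversed only by some other resuscitative action is to be classed, since at present it fits neither class.

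Check the wording of the CRF severity section against the amended definition. Whether the form needs editing cannot be judged from the documents.

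The change concerns classification only. It alters no treatment and no analysis method. The cost is a short protocol wording amendment with the usual IRB/EC approval (Protocol 12.1), a note to sites and, if the form differs, a CRF text correction. Given the small effect, it can wait for the next amendment made for other reasons.
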